Director at MD Anderson and then taken over to Greenpark Pharmacy or will be shipped directly to Greenpark following quality assessment for nicotine concentration using GCMS. Returned or unused study product will be destroyed per institutional guidelines. Avail Vapor and other comparable vendors will supply the e-liquid for use in the eGo ECIG. We will purchase the JUUL devices and JUULpods from a local retailer.

**COVID-19 adaptation:** Participants will be mailed their 3-week allotment of study ECIGs and VLNCCs prior to the start of phases 3 and 4 by a study staff member blinded to the nicotine dose.

**30 Day Follow up Phone Call** Participants will receive a follow-up phone call between ideally 30 and 45 days after the final clinic visit (or scheduled Visit 4 completion date) to assess any open AEs and to complete Timeline Follow-Back since their last visit, however, the end of the window will not close until Timeline Follow-Back is collected or the study ends, whichever is sooner. If the participant became pregnant during the study, this would have been recorded as an adverse event. During this phone call, the research assistant will confirm her due date. This event will remain open until delivery. At that time, the licensed medical professional will contact the participant to ask a few questions about the baby's health and will update the Adverse Event.

**COVID-19 adaptation:** No adaptions required.

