### ***Return Visit Schedule and the Visit Window***

A window will be permissible for all return visits as follows. Ideally, visits 1 to 4 will observe a 7 day window. If the end of the visit window falls on a weekend, holiday, or other day on which the clinic is officially closed, subjects will be allowed to complete the visit during the next business day. If a participant is not able to complete a visit in the preferred window, a maximum window of 1 month between phases will be observed but no deviation will be logged for out of window visits as these are to be expected. A No Show letter may be sent in some cases (see Appendix J). Checkup calls will be conducted around 3 days post Visit 1 and Visit 2 and will have a window of 1 business day. If the call falls on a weekend, holiday, or other day on which the clinic is officially closed, participants will be contacted the next business day. The 30 Day Follow up call will take place ideally between 30 and 45 days after the final clinic visit (or scheduled Visit 4 date), however the end of the window will not close until TLFB data is collected, or the study ends, whichever is sooner. Occasionally, participants ask for a Doctor's Excuse or a Travel Letter, which we may provide at our discretion (see Appendices K and M).

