**Table 4. Study Time Line and Procedures.**

Study Timeframe	Table 4. Study Time Line and Procedures								
	Baseline Screening	Phase 1 Wk 1 (Randomization Visit)	Check -Up Call #1	Phase 2 Wk 2-4	Check-Up Call #2	Phase 3 Wks 5-7	Phase 4 Wks 8-10	30 Day Follow Up Call	
Visit #	0	1		2		3	4	FU Call	
Study Day	-29	1	8	11*	29	32*	50	71	101
ASSESSMENTS									
Phone Screen (Basic Eligibility)	X								
Informed Consent Signed	X								
Pregnancy Test	X	X		X		X	X		
Expired CO†	X	X		X		X	X		
Height	X								
Weight	X	X		X		X	X		
Urine- Compliance (cotinine, TNE, & MA)			X			X		X	
Formaldehyde DNA			X		X		X	X	
Spirometry lung function test†	X							X	
PHQ-9 & GAD-7	X								
Demographics & Smoking History	X								
Medical History	X								
Concomitant Meds	X	X		X		X	X		
Health Changes Questionnaire		X		X		X	X		
Adverse Events		X		X		X	X		
EMA Random Assessments**						X		X	
EMA Daily Diary**					X		X	X	
Product Accountability			X		X		X	X	
TLFB	X	X		X		X	X	X	
ASI-3	X								
CES-D	X								
Mood History	X								
K-6	X								
FTND	X								
MNWS	X	X		X		X		X	
QSU - Brief	X	X		X		X		X	
PANAS	X	X		X		X		X	
American Thoracic Society questionnaire (ATSQ)	X	X		X		X		X	
Purchase Tasks – Usual Brand		X		X		X		X	
Purchase Tasks – Study Cigarette				X		X		X	
Purchase Tasks – E-Cigarette						X		X	
Product Evaluation Scales – Usual Brand			X		X		X	X	
Product Evaluation Scales – Study Cigarette					X		X	X	
Product Evaluation Scales – E-Cigarette							X	X	
Implicit Association Tasks		X		X		X		X	
Perceived Health Risks		X		X		X		X	
Instruct to smoke UB	X								
Receive VLNCC		X		X		X			
Receive e-CLG				X		X			
Flavor Testing†		X							
Support/Troubleshoot				X		X			

\*if call falls on weekend, holiday or other day when the clinic is officially closed, call may be conducted on next business day; \*\*a troubleshooting call may be conducted if reports show at least 2 consecutive days of no EMA data from subject; †procedure waived during COVID-19

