### ***Protection Against Risks***

Our procedures closely follow those used in our previous clinical trials and include medical and psychiatric screening. Our study medical provider will identify participants who are medically unstable and unsuitable for participation in the study. While we expect little procedure related adverse events we will monitor participants for any adverse reactions (related and unrelated) throughout the study (see Appendices HH).

Adverse effects and concomitant medications will be assessed at each of the post-baseline visits. Participants' CO, and weight will also be measured at each in-person assessment. During the COVID-19 pandemic, we will temporarily waive collecting participants'

CO and will collect height and weight via participant self-report. The study medical provider will monitor participants' complaints of adverse events and order any follow-up procedures (laboratory assessments, etc.) as required. Adverse experience assessments will continue until 30 days following completion of the VLNC+ E-Cigarette phase.

Study medical monitor [name] and his team will monitor for respiratory and other adverse events, along with our collaborator from the Department of Pulmonology, [name]. [name] will oversee spirometric interpretation and quality control for the duration of the trial and will be consulted by [name] on respiratory-related AEs, as needed.

Confidentiality will be protected by identifying all subjects by ID numbers in all data used outside the institution (e.g., laboratory assessments). Analyses of such data are provided by sample number coded on each collection container and cannot be connected to individual participant names by the laboratory conducting the assays. Only the PI and his staff will have access to the master file linking laboratory and other data to participant names. All study data files are server maintained with limited access using password entry and log in restrictions to study staff. All information will be reported in aggregate form and individual participants will not be identified in any public reports or documents. We expect these procedures to be highly effective for protecting participant confidentiality.

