#### Adverse Event Monitoring & Concomitant Medication.

Participants will be assessed for side effects and concomitant medications using standard FDA guidelines recommended for these two procedures and recorded into the project database. Adverse event terminology and grades will be determined using the Common Terminology Criteria for Adverse Events (CTCAE), version 4.03, published by the U.S. Department of Health and Human Services.

A response time matrix will be used to guide the medical team on how long they have to respond (immediately to 48 hours) to the notice of an adverse event based on its rating. If someone from the medical team deems it clinically appropriate, the medical team or study staff may provide the subject with patient education materials printed from the MD Anderson database related to the AE they are experiencing. The subject will not be taken off study product unless the study physician or his/her personal physician recommends that we do so. Participants reporting chest pain or chest pressure will be administered a Chest Pain/Chest Pressure questionnaire (see Appendix F.) and will be triaged accordingly.

Adverse events will be reviewed by our medical personnel and the PI. Adverse event monitoring will continue up to 30 days after medication is completed. If an AE is spontaneously reported after the AE reporting period is over, the AE will be recorded in the patient's progress notes. Those AEs that are probably, possibly or definitely related to treatment will be followed until resolution or end of study, whichever comes first. In the case of reports of suicidal ideation, depression or anxiety which we believe may be related to treatment, if possible, we will engage in our normal psychological assessments. The Addiction Psychiatrist will determine the course of clinical management according to methods of good clinical practice. The PI or physician is responsible for determining the attribution of adverse events to study medication.

For this trial, AEs will be recorded according to the Recommended Adverse Event Recording Guidelines for Phase III protocols (see shaded areas of the **Table 5**). Based on the

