Unless otherwise noted, the electronic SAE application (eSAE) will be utilized for safety reporting to the IND Office and MDACC IRB.

Serious adverse events will be captured from the time of the first protocol-specific intervention, until 30 days after the last dose of drug, unless the participant withdraws consent. Serious adverse events must be followed until clinical recovery is complete and laboratory tests have returned to baseline, progression of the event has stabilized, or there has been acceptable resolution of the event.

Additionally, any serious adverse events that occur after the 30 day time period that are related to the study treatment must be reported to the IND Office. This may include the development of a secondary malignancy.

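### AE assessment is promised for 30 days after the last product, but after Visit 4 no scheduled contact is required to ask about new AEs, and late-reported AEs are classified by report date rather than onset date

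*Combined protocol and SAP*

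**What the plan says.** Three sections set the collection period.

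- Protection Against Risks: "Adverse experience assessments will continue until 30 days following completion of the VLNC+ E-Cigarette phase".
- Adverse Event Monitoring & Concomitant Medication: "Adverse event monitoring will continue up to 30 days after medication is completed".
- Serious Adverse Event Reporting: serious AEs (SAEs) are captured "until 30 days after the last dose of drug, unless the participant withdraws consent".

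Four places describe the contacts meant to deliver this.

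- Protection Against Risks puts routine assessment at visits: "Adverse effects and concomitant medications will be assessed at each of the post-baseline visits". The last of these is Visit 4.
- Procedures, under the 30 Day Follow up Phone Call, describes one later contact, "between ideally 30 and 45 days after the final clinic visit (or scheduled Visit 4 completion date) to assess any open AEs". Its other tasks are the timeline follow-back (TLFB) interview and, for a participant who became pregnant, confirming the due date.
- Return Visit Schedule and the Visit Window leaves the upper end of the call window open: "the end of the window will not close until TLFB data is collected, or the study ends, whichever is sooner". The only other scheduled calls are the check-up calls about 3 days after Visits 1 and 2.
- Table 4 puts Visit 4 on day 71 and the follow-up call on day 101. Its "Adverse Events" row appears to carry four marks, consistent with Visits 1 to 4. The TLFB row carries six, consistent with screening, the four visits and the call.

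The AE monitoring section then deals with late reports: "If an AE is spontaneously reported after the AE reporting period is over, the AE will be recorded in the patient's progress notes".

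**The concern.** The stated period and the scheduled contacts do not match. An event that begins after Visit 4 is not open at Visit 4, so a call limited to open events does not ask about it. It enters the record only if the participant raises it. If the participant first raises it at the call, and the call comes after day 30, the late-report rule sends it to progress notes even though it began inside the period.

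At stake is the completeness of the post-product safety record. The protocol names lung injury and other respiratory illness among the possible harms of e-cigarettes, and provides for safety review every six months because of new vaping information. It also already uses AE proportions by phase to argue that the e-cigarette phases are no worse than the cigarette-only phases. AE data used in this way should be collected for the full period the protocol states.

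**Working it through.** This is day arithmetic. No power or sample-size formula applies.

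**Inputs.** Visit 2 = day 29, Visit 3 = day 50, Visit 4 = day 71, follow-up call = day 101 (Table 4). Call window = anchor + 30 to anchor + 45 days (Procedures). AE period = last product + 30 days, reading medication in the AE section as study product.

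**Plan's own figure.** 71 + 30 = 101, which matches the call day in Table 4. The upper end of the ideal window is 71 + 45 = day 116.

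**Completers.**

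- Last product on day 71: the period closes on 71 + 30 = day 101. The call falls 101 − 101 = 0 to 116 − 101 = 15 days after closure.
- Last product on day 70 (end of week 10): the period closes on day 100. The call falls 1 to 16 days after closure.

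Of the 16 possible call days (101 to 116), only day 101 lies inside the period in the first case, and none does in the second. A call delayed until TLFB is obtained falls later still.

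**Worked example.** Last product is on day 71, a non-serious event starts on post-product day 5 (day 76), and the call is on post-product day 35 (day 106). The onset is 25 days inside the period (101 − 76). The report is 5 days outside it (106 − 101). The call is not required to ask about the event. If the participant volunteers it, the late-report rule turns on the date of reporting and sends it to progress notes.

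**People who stop early and attend no further visits.** The call text gives two possible anchors and does not say which applies to whom.

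| Last product and last visit | Period closes | Call, if anchored to scheduled Visit 4 | Call, if anchored to last attended visit |
|---|---|---|---|
| Day 50 (Visit 3) | Day 80 | Days 101–116: 21 to 36 days after closure | Days 80–95: 0 to 15 days after closure |
| Day 29 (Visit 2) | Day 59 | Days 101–116: 42 to 57 days after closure | Days 59–74: 0 to 15 days after closure |

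These stopping days are illustrative. Someone who stops product on day 29 but still attends Visit 3 has an AE assessment 50 − 29 = 21 days later, inside the period, so the table does not describe that person.

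**Result.** After the last attended visit, no scheduled contact falls inside the 30 days before their final day, and the one that follows is not described as asking about new events.

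**The case against.** The case on the other side has several parts, and much of it stands.

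- **A call at the end of the period is sensible.** A retrospective call covering 30 days belongs at or just after day 30. That is right: the timing is not itself a defect. It matters only because the call's stated scope excludes new events and the late-report rule works by report date.
- **Participants can report events themselves.** The section on adverse experiences associated with e-cigarettes says participants will be told to contact staff promptly about symptoms such as cough, shortness of breath or chest pain. An AE volunteered within 30 days is inside the period. A reader might infer that a safety summary must show almost no post-product events. The documents do not support that; they show only that new events are not actively solicited.
- **SAEs are handled separately.** A reader might infer that late-reported SAEs also end up in progress notes. They do not. All SAEs go to the IND Office within 5 working days of knowledge regardless of attribution, and related SAEs that occur after the 30 days must still be reported. A hospitalised lung-injury case would follow that route once known. What remains is that these rules govern events already known to staff and do not ask participants about new ones.
- **Early leavers.** A reader might take the longer delays in the table as fact, or apply the 77% retention reported so far to the enrolment cap of 380 and call the shortfall the number affected. Neither is supported. The anchor is ambiguous, people who withdraw consent are outside the SAE capture promise, some cannot be reached by any call, and the Subject Withdrawal section says every effort will be made to complete required evaluations.
- **Table 4.** Its columns are displaced in the text copy, so the mark count is supporting evidence only. The description of the call and the statement that AEs are assessed at post-baseline visits carry the point.
- **The aims are unaffected.** The statistical section specifies no AE analysis, and the Aim 1 outcomes do not depend on this. That limits the consequence but does not remove the mismatch.

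Staff may well ask about new events in practice. The text does not require it.

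**Conclusion.** The concern holds for active ascertainment of new AEs after Visit 4 and for the recording of non-serious AEs that begin within 30 days of the last product but are first reported later. For completers the ideal call falls 0 to 16 days after the period closes, depending on whether the last product is counted on day 71 or day 70, and it can be later. The number of events lost cannot be estimated from the documents.

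The conclusion assumes that the call's stated AE task is complete as written and that the late-report rule is applied literally. It does not extend to the routing of SAEs, and it does not depend on Table 4. The sections on the follow-up call, visit windows, risk protection, AE monitoring and SAE reporting, together with Table 4, need to be reconciled. This is a gap in the safety record that should be closed; it does not threaten the primary comparison.

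**What to change.** 1. In Procedures (30 Day Follow up Phone Call) and in Table 4, state that the existing call asks about any new AE or SAE since the last contact, as well as open ones.
2. In Adverse Event Monitoring & Concomitant Medication, decide entry to the AE database by onset date, that is, onset within 30 days of last product use, whatever the date of report. Progress notes would then be kept for AEs with onset after that period, with the existing SAE rules unchanged.
3. In Procedures and in Return Visit Schedule and the Visit Window, state which anchor applies to participants who stop early, remain contactable and have not withdrawn consent. Tie it to last product use so that it matches the 30-day period in the AE and SAE sections.

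Reading the respiratory symptom questionnaire over the phone at this call would be an optional extra and is not needed to resolve the mismatch.

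The cost is protocol wording, one mark in Table 4, a few more minutes on a call already being made and a few more AEs to enter.

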## Measures

**In-person assessment of product use, smoking behavior, and withdrawal.** At each in-person or virtual session, participants will provide a urine sample to measure TNE and MA, and provide expired CO (except at screening, where urine for TNE/MA is not collected because participants are not on study product yet). If the session is conducted virtually, expired CO will not be collected. Research assistants will also complete a Time Line Follow Back (TLFB [99]) interview to record nicotine product use up to 30 days before screening and/or up to and including last contact, including CPD (VLNCC and own brand) and number of e-cig sessions per day. The *primary* measure of CPD will come from the daily diary data. TLFB will be used as a secondary source to supplement missing data. Participants will be required to return used and unused VLNCC packs and e-cig cartomizers at each session for compliance/accounting analysis. Cartomizer weight, before distribution and upon return will provide an estimate of total product use, which will be used in conjunction with the diary data. Participants will also complete a computerized battery of questionnaires, including nicotine withdrawal (Minnesota Nicotine Withdrawal Scale; MNWS [100]), craving (Questionnaire of Smoking Urges-Brief; QSU-Brief [101]) and affect (Positive and Negative Affect Scales; PANAS [102]). Unlike the diary data which is obtained daily, or the EMA assessments that occur in real-time, these questionnaire measures cover broader segments of time (i.e., past 7 days). Missing assessments or items are expected and acceptable and are not considered a protocol deviation/violation.

**COVID-19 adaptation:** We will ask participants to collect and ship their urine samples to us using postage-paid supplies that we will mail to them. TLFB will be collected virtually by study staff. We will also provide postage-paid shipping supplies for participants to return all used and unused VLNCC packs and e-cig cartomizers or JUUL pods. Questionnaires will continue to be administered electronically via the institutionally-approved web-based Qualtrics platform administered over the study smartphones. However, due to the restrictions in place limiting community and employee access to MD Anderson's campus, we will temporarily waive CO collection. CO collection will resume when MD Anderson has moved to a phase in which community participants are permitted on campus and in the Behavioral Research Treatment Center (BRTC) in the Duncan Building (or at another approved on-campus or offsite location).

**In-person assessment of explicit product liking.** Self-reported liking will be measured at the end of each phase using Product Evaluation Scales (PES), which are modified versions of the Cigarette Evaluation Scale (CES [103]). The CES is an 11-item questionnaire that evaluates the cigarette smoking experience in terms of satisfaction, good taste, dizziness, ability to calm, concentration, wakefulness, reduction of hunger, nausea, irritability, enjoyment of sensations of smoke, and craving reduction. We will use 3 versions of the PES to evaluate usual brand, VLNCC, and ECIG product liking (see Appendix T). To assess perceived product harm, we will administer modified Perceived Health Risks questionnaires (PHR) that will assess beliefs about the addictiveness and health consequences of own brand, VLNCC, and ECIG products (see Appendix X).

COVID-19 adaptation: No adaptations needed. These questionnaires are currently administered electronically using Qualtrics over study smartphones.

**In-person assessment of implicit product liking.** At the end of each product exposure phase, participants will complete Implicit Association Tests (IAT) designed to evaluate attitudes towards usual brand, VLNCCs, and ECIGs (see Appendix U). The IAT has been used to evaluate attitudes toward consumer products [104, 105] and is comprised of two tasks. In the first task, participants are instructed to rapidly distinguish between two paired products and attributes (e.g., cigarettes + good vs. e-cigs + bad) using two assigned response buttons. In the second task, the pairings are switched. By calculating a standardized difference score between the reaction time differences, one can determine which products and attributes are more strongly associated in memory, thus determining whether an individual has a relatively more positive or negative attitude toward one product vs. the other [106]. We have substantial previous experience with this task using established methods [107] in our studies. For each of the 3 products of interest, we will create 24 pictures that minimize product branding. The good and bad attribute words will come from a previously published set from our lab [108]. To score the IAT, we use the standardized difference score method recommended by Greenwald and colleagues whereby the standardized difference score (D) between mean response times per trial are computed and divided by the pooled SD [109]. Each IAT product comparison will take approximately 8 minutes to complete.

COVID-19 adaptation: We will adapt the IAT to a web-based platform, and will ask participants to complete the task electronically by accessing a hyperlink using the study smartphone.

**In-person assessment of product Relative reinforcing efficacy (RRE) using purchase tasks (PT).** At the end of each phase, participants will complete 3 hypothetical PTs (see Appendix V). PTs are behavioral economic reward valuation tasks that have been used to assess the RRE of food [110], alcohol [111], illicit drugs [112], and nicotine products [113]. The PT provides an estimate of how much a participant is willing to pay (i.e., its valuation) for a given product (VLNCC, UB, ECIG) over a range of unit price intervals (\$0.01 to \$1,000). Responses will be used to compute five demand indices, including breakpoint (first price at which consumption goes to zero, i.e., unwilling to pay), demand intensity (consumption at the lowest price),  $O_{max}$  (maximum financial expenditure on the product),  $P_{max}$  (price at which expenditure is maximized), and elasticity of demand (sensitivity of product consumption to increases in cost). These relative values will be compared across the different products to determine their RRE.

COVID-19 adaptation: Study staff will administer the purchase tasks during the virtual "in-person" sessions with participants using an institutionally approved platform, such as Zoom.

**Smartphone Assessments of Withdrawal, Craving, Affect, Satisfaction, Frequency, and Duration of Product Use.** Two categories of smartphone assessments will be implemented. One is a limited daily diary assessment which occurs only once per day, and will

provide measures of product use (CPD; e-cigarette puff count from device), withdrawal, craving, affect and satisfaction (reinforcement). The other is a random EMA assessment that will occur twice a day and will provide real-time measures of these same constructs (see Appendix II). To limit assessment burden, once daily diary assessments will occur in phases 2, 3, & 4, whereas by design, the user initiated and random EMA assessments occur only in phases 3 & 4. In the U54 preliminary study, an interactive voice response system was used to collect daily CPD. Here, we use the smartphone-implemented diary to collect CPD because we believe that it will provide superior reliability, as well as other advantages described below. The random EMA assessments are limited to phases 3 & 4 because our *primary* interest in these assessments is to longitudinally explore withdrawal, craving, affect and satisfaction related to dual product use among DS and ITS, including the differential effects of ECIG dose. EMA while smoking regular cigarettes has been thoroughly studied in DS and ITS by Shiffman and colleagues [70, 71, 73, 75, 76] and need not be replicated here.

Our smart phone assessments are modeled after several of our previous studies in which we enrolled very diverse smoking populations [88, 90, 94]. We will make modifications to accommodate the ITS as outlined by Shiffman [70, 73] and provide training to participants relevant to each assessment type and study phase (see Appendices PP and RR).

The daily diary assessments will occur 30 minutes after waking and will assess 6 measures from the previous day, including CPD (VLNCC/UB), 8 items based on the QSU, PANAS and MMWS to assess withdrawal, craving, affect (negative and positive) and satisfaction. For the random EMA assessments (phases 3 & 4 only), participants will be prompted to complete up to 2 assessments associated with product use (based on smoking rate-see below). To enhance compliance, the smartphone will provide immediate feedback, as described in the compensation section below.

For the random assessments, each day will be divided into 2 blocks. Within each block, 1 EMA assessment will be randomly triggered to assess withdrawal, craving, affect, and reinforcement. The software prevents random assessments from occurring within 15 minutes of other assessments. Because prompts may occur at inconvenient times, participants can choose to not participate in that random assessment.

EMA "booster trainings" are provided at all in-person or virtual visits [114].

Total time devoted to EMA is fairly reasonable (between 10-15 minutes/day on average), with compliance rates observed of >75% in our previous research and that of others [88, 90, 94]. Our previous research has shown EMA reactivity is nonexistent or small [115]. We have extensive experience implementing and developing EMA programs and analyzing EMA data related to smoking behavior and anticipate no issues in carrying out this aspect of our proposal [88, 90, 94, 116, 117].

COVID-19 adaptation: No adaptations needed.

**Other Important Smartphone Features.** This will include automatic real-time download of data to our secure server, appointment and specimen collection reminders (see biomarkers below), as well as the option to call/ text participants if expected data are not forthcoming (e.g., no diary input on a given day). If reports show no EMA data for at least 2 consecutive days, study staff may contact the participant to troubleshoot.

COVID-19 adaptation: No adaptations needed.

**Financial Compensation for Behavioral Assessments.** Participants may earn \$40 for completing assessments at each in-person or virtual visit; \$10/phase for returning home-collected urine samples; \$2/instance for completing daily diaries (done only once per day) in

phases 2 – 4; and \$3/instance for completing EMA assessments (completed up to 2 times/day) in phases 3 and 4; \$10 for completing questionnaires electronically prior to the study visit and \$30 for returning their study phone in working order (including the accessories that were issued with the phone like charger, cord, case and screen protector, etc.). Because the total possible compensation is greater than \$600, subjects will be asked to complete a W-9. Study staff will inform the appropriate contact in the MD Anderson Treasury Services/Tax Compliance when a subject reaches the \$600 threshold and will provide the W-9 for reporting purposes. Subjects will be informed that the study payments are considered taxable income and reportable to the Internal Revenue Service (IRS). A Form 1099 will be sent to the subject if their total payments are \$600 or more in a calendar year.

COVID-19 adaptation: No adaptations needed.

**Financial Compensation for VLNCC compliance.** We know from our U54 that some participants smoked UB cigarettes during the VLNCC condition (~2-3 CPD). However, the effect of non-compliance was negligible, as TNE, our primary measure of nicotine compensation, dropped significantly by week 3 relative to UB smoking (See **Figure 1**). Such would be the case here as well, although in this study we will provide incentives for VLNCC compliance. In our recent unpublished inpatient study, 23 smokers smoked only VLNCC 0.03 mg cigarettes for one week, while 7 others were permitted to "cheat" by allowing them to smoke 1-2 UB cigarettes in addition to the VLNCC's. We determined that a 0.02 nmol/ml cut-off for anatabine (a minor tobacco alkaloid) would identify non-compliance with smoking the 0.03 VLNCC exclusively, by as few as 1-2 UB cigarettes. Anatabine is derived from tobacco and is not affected by e-cig use, whereas TNE is influenced by nicotine from either combustible or non-combustible sources. Thus, anatabine provides an excellent measure of VLNCC compliance. Subjects will be told that compliers (<0.02 nmol anatabine) will receive a \$100 bonus in phases 2 (VLNCC) and 3 & 4 (VLNCC+ECIG). Honest reporters of UB above this level will receive a \$10 bonus, while those above this level who do not report UB use will receive no bonus.

COVID-19 adaptation: No adaptations needed.

**Sample collection and biomarker analyses.** A urine sample (TNE and MA) will be obtained at each visit starting at Visit 1. In addition, participants will be asked to collect a urine sample at home twice a week between appointments, which will be collected at their subsequent appointment. This will allow for better assessment of TNE and MA exposure among low frequency smokers. Smartphones will be used to prompt the participant to obtain the sample. If the participant fails to bring in any/all samples, a deviation will not be logged. A spot urine collection will be conducted during the visit in the event no samples are returned. Urine samples will be sent to the University of Minnesota for analysis. Samples will be de-identified containing only the subject ID generated by the study database, visit number, code corresponding to type of sample, vial number and date collected (example, 456123-03-2-5 9/1/2018).

COVID-19 adaptation: Participants also will be asked to collect a urine sample at home on or near the day of their virtual "in-person" visits, starting at Visit 1. For ease of remote collection, we will only ask for participants to complete one urine collection on or near the time of their visit. We will provide postage-paid supplies for participants to ship these samples to the study team for proper storage and analysis.

Total Nicotine Equivalents (TNE) is the sum of total nicotine, total cotinine, total 3'-hydroxycotinine and nicotine N-oxide excreted in urine ("total" refers to the analyte and its glucuronide conjugate) comprise 85 to-95% of the nicotine dose received by a tobacco user [118], and is an excellent biomarker of nicotine uptake, directly measuring a high percentage of the nicotine dose. TNE will be analyzed by liquid chromatography-electrospray ionization-

tandem mass spectrometry (LC-ESI-MS/MS) [119, 120]. Use of TNE will enable us to quantify changes in nicotine exposure through each phase of the study and will be *our primary measure of nicotine compensation between baseline and subsequent conditions*.

Minor Tobacco Alkaloids (MA) will be analyzed using the LC-ESI-MS/MS method [121, 122]. While nicotine is accepted as the major addictive compound in tobacco, several other constituents, such as MA (e.g., anabasine, anatabine, and nornicotine), may also play a role, and the potential differences in these compounds as a function of ECIG and VLNCC use is of interest. *MA will allow us to estimate differential use in combustible vs. e-cig use, and anatabine will allow us to determine smoking of VLNCC vs. UB.*

Quality Control Procedures. Multiple urinary aliquots will be prepared, labelled, and frozen. With each set of samples, 2 aliquots are analyzed. If the results from these 2 aliquots do not agree within 10% of the known amount, then that set of samples is reanalyzed. Negative controls are also included with each set analyzed.

Acrolein DNA Adduct. A supplement was originally approved to quantify the formaldehyde DNA adduct N-hydroxymethyldeoxyadenosine (N-HOMe-dAdo) in leukocyte DNA samples collected using cheek swabs, but this was changed to the acrolein DNA adduct 8R/S-3-(2'-deoxyribos-1'-yl)-5,6,7,8-tetrahydro-8-hydroxypyrimido[1,2-a]purine-10-(3H)-one ( $\gamma$ -OH-Acr-dGuo) after instrumentation problems experienced by our collaborator. Measuring this acrolein DNA adduct would provide us with a measure of carcinogenesis specific to e-cigarettes [123]. It would complement the biomarkers of combustible tobacco and nicotine exposure that are included as part of this original funded R01, including total nicotine equivalents (TNE; the sum of nicotine, cotinine, 3'-hydroxycotinine and their glucuronide) and minor tobacco alkaloids (MA; i.e., anabasine, anatabine, and nornicotine). A cheek swab will be collected at Visits 1, 2, 3, and 4. Saliva samples will be sent to the University of Minnesota for analysis. Samples will be de-identified containing only the subject ID generated by the study database, visit number, code corresponding to type of sample, vial number, and date collected (e.g., 456123-03-2-5 9/1/2018).

**COVID-19 adaptation:** Participants will be asked to collect a saliva and/or cheek swab sample at home on or near the day of their virtual "in-person" visits 1, 2, 3, and 4. We will provide postage-paid supplies for participants to ship these samples to the study team for proper storage and analysis. Pending approval by MD Anderson's Research COVID Leadership Team (RCLT), community participants who can provide saliva mouthwash and/or cheek swab sample at an approved collection site will be asked to do so within a week of their scheduled virtual "in-person" visits 1, 2, 3, and 4. Approved sites may include University of Texas MD Anderson, University of Texas sister institutions, other universities or hospitals located in Texas, and/or contracted commercial vendors. Until approval is provided we will suspend collection of these samples, but continue all other aspects of the study.

**Assessment of respiratory and other symptoms.** For safety reasons, we will assess respiratory health at baseline and at the final study visit using a CareFusion Vmax Vnytus PC-based spirometer (Höchberg, Germany) without a bronchodilator trial (including forced expiratory volume in 1 second [FEV1], forced vital capacity [FVC], the FEV1/FVC ratio, and peak expiratory flow rate [PEFR]) that will be administered by study staff trained per American Thoracic Society guidelines [124] under the supervision of collaborator [name] from the Department of Pulmonary Medicine. [name] will oversee spirometric interpretation and quality control for the duration of the trial. We will also assess respiratory symptoms at each visit using the American Thoracic Society questionnaire (ATSQ) [125]. The ATSQ is an 8-item questionnaire that assesses symptoms including coughing, wheezing, phlegm production, and shortness of breath. Study Medical Monitor [name] will oversee the collection, review,

and attribution of adverse events (AEs) in this study and will consult with [name] on respiratory-related AEs, as needed.

COVID-19 adaptation: Due to the restrictions in place limiting community and employee access to MD Anderson's campus, we will temporarily waive the inclusion/exclusion criteria related to spirometry (willing and able to complete two spirometry sessions; bronchial or respiratory infection in the last 14 days; subject's spirometry FEV1 percentage reading is <50 [severe to very severe obstruction]). Similarly, visit procedures related to spirometry also will be temporarily waived. The spirometry inclusion/exclusion criteria and visit procedures will be reinstated when MD Anderson has moved to a phase in which community participants are permitted on campus and in the Behavioral Research Treatment Center (BRTC) in the Duncan Building (or in another approved on-campus or offsite location), and spirometry for research purposes has been deemed safe by the institution.

